7.9. Study Procedures

7.9.1. Informed Consent

Prior to initiation of any study related procedures, patients will review and sign the study's informed consent form to participate in the study after having been informed about the nature and purpose of the study, participation and termination conditions, and risks and benefits.

7.9.2. Randomization

At Day 1, after confirmation of eligibility and completion of all required assessments per Table 7-2, blinded site personnel will randomize eligible patients within the randomization module in a 1:1 ratio.

7.9.3. Review of Eligibility, Medical History, Prior Treatment and Medications

Eligibility criteria (inclusion and exclusion criteria), medical history (including OA history), prior treatment and medications are reviewed during Screening and at Day 1 per the schedule noted in Table 7-2.

OA medical history includes ACR diagnosis details, OA diagnosis date (if available), number of days with index hip pain in the last month, previous IA steroid, PRP or hyaluronic injections, presence of OA in other joints, prior procedures or surgeries for index hip OA.

At Day 1, eligibility should be confirmed (inclusion/exclusion criteria review against any new information/findings through Day 1 assessment).

7.9.4. Physical Examination

The physical exam will assess the following body systems:

- General Appearance
- Skin
- Lymphatics
- HEENT (head, ears, eyes, nose, throat)
- Cardiovascular
- Respiratory
- Abdominal
- Musculoskeletal
- Neurological

Physical exams are to be conducted at the days indicated in Table 7-2 and Table 7-3.

Any clinically significant findings must be documented in the source and added to the medical history if found at Screening or recorded as an AE if new or worsened from baseline at one of the post-baseline visits.

CONFIDENTIAL Page 50 of 72

7.9.5. Index Hip Assessment

The index hip assessment will be performed by the blinded assessor at the days indicated in the Table 7-2 and Table 7-3. The index hip will be assessed for tenderness, warmth, redness, swelling, and effusion, limitation on range of motion (directions: flexion, extension, abduction, adduction, internal rotation or external rotation; severity: mild, moderate or severe). If there is a clinically significant finding at the Screening or Day 1 Visit (pre-injection), add to the Medical History. At time points post-injection, if there are new clinically significant findings or findings that worsen for the patient's baseline condition, record as AEs.

7.9.6. Index Hip X-ray

A diagnostic quality X-ray of the index hip is required (weight-bearing anterior-posterior pelvic view with the lower limbs in 10 degree internal rotation with a size ratio of 1:1) at Screening, Week 12 and End of Study Visit (for patients who receive an open-label injection of FX006) (see Table 7-2 and Table 7-3).

The Screening X-ray will be read centrally for K-L grading and potential risk signs of rapidly progressive OA (e.g., atrophic osteoarthritis, femoral head necrosis and/or collapse, subchondral bone insufficiency fracture, etc.). In addition to the Screening X-ray, the Week 12 and End of Study X-rays will be read centrally. An image acquisition protocol will be distributed to sites with instructions for radio-anatomic positioning for reliable grading.

Kellgren-Lawrence grading is a global scoring method that considers osteophytes, JSN, subchondral bone sclerosis and/or bone attrition. Grading criteria for the hip are (Rheumatology 2005;44 Suppl 4:54):

Grade 0: Normal appearance.

Grade 1: Possible osteophytes, possible JSN medially.

Grade 2: Definite osteophytes, definite JSN, slight sclerosis.

Grade 3: Mild osteophytes, marked JSN, moderate sclerosis, cysts and deformity

Grade 4: Large osteophytes, severe JSN, cysts sclerosis and deformity

Subjects will be considered radiographically eligible for enrollment in the study if the (index) hip is Kellgren-Lawrence Grade 2 or 3.

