7. INVESTIGATIONAL PLAN

7.1. Overall Study Design and Plan

This is a two-part, multi-center, randomized, double-blind, placebo-controlled, parallel-group study in patients with hip OA. Approximately 70 patients will be enrolled in Part I and approximately 440 patients will be enrolled in Part II of the study. In each part, patients will be randomized to one of two treatment groups (1:1) and treated with a single IA injection of either 32 mg FX006 or normal saline.

Eligible patients will be randomized within strata defined by Baseline Western Ontario and McMaster Universities Osteoarthritis Index (WOMAC) A (pain) (0-10 numeric ratings scale (NRS) average of Screening 2 and Day 1 with the following classifications: 5.0 to < 6.0, 6.0 to < 7.0, and $\geq 7.0 \text{ to} 9.0$ (see Section 9 for details).

FX006 or saline placebo will be administered as a single IA injection with a 12-week follow-up period in the double-blind phase.

Patients participating in Part I of the study will be treated with a single IA injection of either 32 mg FX006 or normal saline and will return for follow up visits at Weeks 12, 16, 20, and 24 or up until the time of this amendment. The patients will be discontinued at the time of notification by the Investigator.

Patients participating in Part II of the study will be treated with a single IA injection of either 32 mg FX006 or normal saline and will return for follow up visits at Weeks 12, 16, 20, and 24. Patients who are eligible for the second injection in the open-label phase at Week 12 will receive an open-label injection of FX006 at Week 12 and return for follow-up visits at Weeks 16, 20, and 24. These patients will complete the study at Week 24.

Patients participating in Part II of the study that are not clinically indicated for a second injection at Week 12 will return to the clinic at Weeks 16, 20, and 24 and will receive an open-label injection of FX006 at the first evaluation where the patient has been determined to meet all criteria. Patients will then return for follow-up visits every 4 weeks for 12 weeks post second injection and will complete the study 12 weeks post second injection (e.g., Week 24, 28, 32, or 36 depending on when the patient receives the open-label injection).

Patients participating in Part II of the study who are not eligible for a second injection after evaluation at Weeks 12, 16, 20, and 24 will complete the study at the Week 24 visit and complete the End of Study (EOS) assessments.

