7.4.3. Exclusion Criteria

Patients fulfilling at least one of the following criteria may not be included in the study:

Disease-related criteria

- 1. Patients who cannot washout of prohibited medications (e.g., opioids or other analgesics) (Refer to Section 7.6.2)
- 2. Diagnosed as secondary OA in the index hip including but not limited to articular fracture, major dysplasia or congenital abnormality, osteochondritis dissecans, acromegaly, ochronosis, hemochromatosis, Wilson's disease, or primary osteochondromatosis, etc.
- 3. Current or any history of ipsilateral chronic knee pain (lasting \geq 3 months)
- 4. Contralateral hip and/or knee pain ≥ 4.0 (0-10 NRS scale) within 1 month prior to Screening visit
- 5. Current or any history of chronic Sciatica (lasting \geq 3 months)
- 6. Current or any historyof acetabular labrum tear in the study hip
- 7. Atrophic osteoarthritis, femoral head necrosis and/or collapse, or subchondral bone insufficiency fracture in the index hip joint determined via central reading
- 8. Current or history of infection in the index hip (e.g., osteomyelitis) or current skin infection at injection site
- 9. Concurrent chronic pain conditions with pain score ≥ 4.0 (0-10 NRS scale) within 1 month prior to Screening 1 visit, including but not limited to:
 - hip impingement syndrome, trochanteric bursalgia
 - peripheral or central neuropathy that may affect sensation of the index hip
 - non-radicular low back pain
 - peripheral nerve entrapment
 - diabetic neuropathy
 - post-herpetic neuralgia
 - post-stroke pain
 - fibromyalgia
- 10. Major surgery or clinically significant trauma (e.g., fracture) of lower limbs within 12 months prior to Screening visit or with ongoing sequelae.
- 11. painDETECT Questionnaire (PD-Q) score > 18 during Screening visit
- 12. History or current evidence of reactive arthritis, rheumatoid arthritis, psoriatic arthritis, ankylosing spondylitis, or arthritis associated with inflammatory bowel disease, systemic lupus erythematosus or other autoimmune diseases
- 13. Any planned surgeries in the lower limbs during the study period

CONFIDENTIAL Page 35 of 72

Previous or concomitant treatment-related criteria

- 14. Presence of surgical hardware or other foreign body in the index hip
- 15. Planned/anticipated surgery that would require use of a restricted medication during the study period
- 16. IA corticosteroid of any joint within 3 months of Screening visit (investigational or marketed, including FX006)

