7.4.4. Second Injection Inclusion Criteria (Part II Patients Only)

To be eligible to receive the second injection during the open-label phase, patients must fulfill the following criteria:

- 1. Completed the double-blind phase of the study through Week 12
- 2. No major safety concerns during the initial dose period (including allergic reaction to initial dose of study medication) as assessed by the Investigator and patient
- 3. Clinically indicated to receive FX006, in the opinion of the Investigator and patient
- 4. WOMAC A (pain) score of ≥ 3 (0-10 NRS)
- 5. Compliant with study procedures and visit schedules up to the open-label injection with FX006 and the willingness and ability to continue to comply for additional 12 weeks after the second injection
- 6. Willingness to continue abstaining from use of protocol-restricted medications during the study (Refer to Section 7.6.2)

CONFIDENTIAL Page 37 of 72

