7.8. Schedule of Study Assessments

A summary of the schedule of assessments is provided in Table 7-2 and Table 7-3. Refer to Section 7.9 for details of each assessment.

CONFIDENTIAL Page 47 of 72

Table 7-2: Schedule of Study Assessments for Double Blind Phase

List of Assessments	Screening 1 ⁿ Day -30 to -1	Screening 2 ⁿ Day -10 to -4	Day 1	Weeks 1, 4, 8 ^m	Week 12 EOS for Double blind phase ^{a, m}
Informed consent	X				
Inclusion/Exclusion Review	X		X ^b		
Medical History/Update	X		X ^b		
Patient Demographics	X				
OA Medical History	X				
Prior Treatments and Medications	X		X^{b}		
Physical examination	X				X
Index Hip Assessment	X		X ^b	X	X
Index Hip X-ray ^c	X				X
Vital signs	X		X ^b	X	X
Height	X				
Weight and BMI	X				X
Hematology, Chemistryh	X				X
ESR	X				
HIV, Hep B/Ch	X				
Pregnancy Test ^f	X ^h		X ^b		X
Washout of restricted pain medication	X ^d				
PD-Q, PHQ-9, GAD-7, PCS, ISI	X				
Randomization			X^{b}		
Second Injection Criteria					X
Index Hip Aspiration			$X^{b, g}$		
IMP administration ⁱ			X		
Rescue Medication dispensing and	Х		X	X	X
accountability ^e	Λ		Λ	A	Λ
Accurate pain reporting and placebo		X	X^{b}	X	X
response reduction training j		N/		77	V.
WOMAC ^k		X	X ^b	X	X
PGIC ^k				X	X
TSQM-9 ^k			L		X
SI, HOOS-QOL, EQ-5D-5L ^k			X ^b	X	X
AE/SAE & ConMeds ¹					X

- a. *The Double-Blind Phase* of the study ends at Week 12. Patients participating in Part I of the study will not receive a second injection but will return to the clinic at Weeks 12, 16, 20, and 24 or up until the time of this amendment. Patients participating in Part II of the study who are eligible for the second injection in the open-label phase at Week 12 will receive an open-label injection of FX006 at Week 12 and return for follow-up visits at Weeks 16, 20, and 24. These patients will complete the study at Week 24. Patients participating in Part II of the study who are not clinically indicated for a second injection at Week 12 will return to the clinic at Weeks 16, 20, and 24 and will receive an open-label injection of FX006 at the first evaluation where the patient has been determined to meet all criteria.
- b. To be collected or assessed prior to injection of study medication
- c. X-ray of weight-bearing anterior-posterior view for index hip will be taken for central reading.

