7.9.11. Second Injection Criteria

Second Injection Inclusion and Exclusion Criteria must be assessed prior to administration of second injection of study medication. Please reference Section 7.4.4 and Section 7.4.5 for Second Injection Inclusion/Exclusion criteria listing. Please also reference Table 7-3.

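### In Part II, open-label FX006 can be injected at the Week 12 visit before that visit's hip X-ray is centrally read, and no second-injection criterion names the lesions that bar entry

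*Protocol*

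**What the plan says.** **Entry.** Exclusion 7 in Protocol 7.4.3 bars "Atrophic osteoarthritis, femoral head necrosis and/or collapse, or subchondral bone insufficiency fracture in the index hip joint determined via central reading". Section 7.9.6 has the Screening film read centrally for Kellgren-Lawrence grade and for "potential risk signs of rapidly progressive OA", and its examples are these same lesions.

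**Films.** Section 7.9.6 requires an index hip X-ray "at Screening, Week 12 and End of Study Visit (for patients who receive an open-label injection of FX006"). On reading, it adds: "In addition to the Screening X-ray, the Week 12 and End of Study X-rays will be read centrally". It gives no time by which the result must return.

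**Second injection (Part II only).** Table 7-2 places the Week 12 X-ray and the second-injection criteria at the same visit. Its footnote a says that patients "who are eligible for the second injection in the open-label phase at Week 12 will receive an open-label injection of FX006 at Week 12". Section 7.1 brings those not indicated at Week 12 back at Weeks 16, 20 and 24; each of them "will receive an open-label injection of FX006 at the first evaluation where the patient has been determined to meet all criteria". The injection column of Table 7-3 has no X-ray entry, and its footnotes let a Week 12 injection share the assessments of the double-blind Week 12 visit.

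**Checks before dosing.** Section 7.9.11 says: "Second Injection Inclusion and Exclusion Criteria must be assessed prior to administration of second injection of study medication". Those criteria are the 6 inclusions in 7.4.4 and the 10 exclusions in 7.4.5. The closest ones are:
- inclusion 2: "No major safety concerns during the initial dose period"
- inclusion 3: clinical indication, in the opinion of investigator and patient
- exclusion 10: an investigator-judged catch-all for conditions that rule out an intra-articular steroid or endanger the patient.

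**The concern.** The protocol treats these lesions as serious enough to bar a first injection, on a central reading. It then takes another film at Week 12, sends it for central reading, and lets the next steroid injection go ahead at that visit whether or not the result is back. The film that could show a new lesion is in hand, but the plan does not require its result to be used.

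The primary objective of the open-label phase (6.3.2) is the safety of a second injection. For saline-arm patients, this injection would be their first FX006 dose.

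Clinical findings may not fill the gap. A second injection requires a WOMAC A score of at least 3 and a clinical indication, so it goes to patients whose hips still hurt. Under 8.2.3, a gradual return of index-hip pain is not an adverse event unless it is clinically significantly worse than baseline. That a new structural lesion could look like ordinary persisting pain is my inference; the documents do not say so.

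**Working it through.** **1. The plan's own figure.** The point rests on no efficacy calculation, but the 6% discontinuation rate in 9.3.1 is used for scope, so I checked how the plan applies it. With a difference of 0.65, SD 2.0, two-sided alpha 0.05 and 90% power:

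n = 2 × 2.0² × (1.960 + 1.282)² / 0.65² ≈ 199 per arm; 199 / 0.94 = 211.7, rounded up to 212.

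This reproduces the stated 212. The 6% is applied to a Week 12 endpoint, so I read it as loss before Week 12.

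**2. Scope.** Part II plans about 440 patients.
- Reaching Week 12: 440 × (1 − 0.06) = 413.6, about 414.
- From the saline arm, if discontinuation is equal: 413.6 / 2 = 206.8, about 207.

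These are ceilings on the number who could be considered for a Week 12 injection. The share injected at that visit is not given, and the pain and indication criteria can only lower it.

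**3. Age of the latest film at each injection visit.** Film age = injection week − 12: 0, 4, 8 and 12 weeks for Weeks 12, 16, 20 and 24. No film is scheduled between Week 12 and End of Study.

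**4. The decision points side by side.**

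| | First injection | Second, Week 12 | Second, Weeks 16–24 |
|---|---|---|---|
| Latest film | Screening | same visit | 4 to 12 weeks old |
| Time for a central read | screening period of 10 to 30 days (7.1.1) | none provided | several weeks |
| Read required before dosing | yes, exclusion 7 depends on it | not stated | not stated |
| Lesion named as disqualifying | yes, exclusion 7 | no | no |

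**5. Reading the criteria one by one.** The inclusions cover completion of Week 12, safety concerns, clinical indication, pain score, compliance and abstaining from restricted drugs. The exclusions cover hip infection or crystal disease, other intra-articular procedures, immune-acting or chemotherapy drugs, live vaccines, other investigational products, recent antibiotics, skin breakdown, pregnancy, contraception and the catch-all. None mentions an X-ray, a central read or any exclusion-7 lesion.

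**6. Result.** At Week 12, both the named criterion and the time for the read are missing. At Weeks 16 to 24, only the named criterion is missing.

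**The case against.** The strongest reply is that the second-injection criteria must be assessed before dosing, and that a reported femoral head necrosis or insufficiency fracture falls readily under inclusion 2, inclusion 3 or exclusion 10. Section 8.2.1 has the investigator review diagnostic results, the index hip is examined at the visit, the injection is done under fluoroscopy, and 7.1 allows the injection to wait for a later visit. Other entry exclusions are also not restated in 7.4.5, so leaving one to a catch-all may be a drafting choice.

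For Weeks 16, 20 and 24 this largely stands. A reader might infer that the gap is equally serious at those visits. The documents do not support that: the film is at least 4 weeks old, nothing suggests the read would still be outstanding, and the general criteria would probably exclude a reported lesion, although by judgment and not by rule.

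For Week 12 it does not stand. These criteria and the review of results can act only on a result that is known. The hip assessment records clinical signs and range of motion, and fluoroscopy is specified to guide the needle. An investigator may choose to wait, but nothing in the available text requires it.

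Three further limits are fair:
- Figure 1 (the Part II flow chart), the image acquisition protocol and a Part II SAP were not available, so a hold written only there cannot be ruled out.
- Section 5.2.8 expects further protocol changes, and Part I analyses are to finish before Part II enrols. The gap is therefore prospective; Part I patients receive no second injection under this version.
- The knee data are reassuring as far as they go: section 5.2.7 reports no treatment-emergent insufficiency fracture, subchondral bone change or osteonecrosis in FX006-treated patients at Week 24. That is a different joint after a single injection.

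**Conclusion.** The point holds for the Week 12 injection. Followed as written, the plan permits FX006 into a hip with a new lesion that would have barred entry, before the film from that visit has been read. For later injections, what remains is the lack of a named criterion, which is a lesser matter.

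The scope is at most about 414 patients reaching Week 12, about 207 of them from the saline arm. This assumes that all of the 6% leave before Week 12 and that losses are equal between arms.

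Two stronger readings should be resisted:
- *A number of harmed hips.* The documents give no hip lesion rate, and the knee finding does not supply one. I project no count.
- *A Week 12 read form that lacks exclusion-7 items.* SAP 4.11.4 lists neither atrophic osteoarthritis nor femoral head collapse among its follow-up variables. But its Screening list omits them too, although exclusion 7 depends on a central read for them. The list therefore cannot be taken as everything the reader assesses, and this SAP covers Part I only.

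The double-blind primary endpoint is not affected. This is a safety gap worth closing before Part II opens. Confidence is medium because of the material not seen.

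**What to change.** 1. **Add an exclusion to 7.4.5:** any entry-exclusion-7 finding on the central read of the Week 12 X-ray.
2. **Add a hold to 7.9.6 and 7.9.11:** the safety read of the Week 12 film must reach the investigator before the second injection, at whichever visit that falls.
3. **Define an injection window after Week 12.** Leave the Week 12 assessments as they are and do not repeat them. Set the window's length to the read turnaround agreed with the central readers, and count follow-up from the actual injection date.
4. **Specify the injection-day checks.** Do the index hip assessment, vital signs, pregnancy test where applicable, and aspiration. Recheck the time-sensitive second-injection exclusions: 1 (hip infection or crystal disease), 6 (recent antibiotics) and 7 (skin breakdown).

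**Cost.** Protocol wording and an agreed turnaround; no new film or reader. The turnaround is not given in the documents. SAP 4.11.4 describes two independent follow-up readings, with third-reader adjudication of some findings, so a result within the ±3 day visit window should not be assumed. Patients may face a delay of days or an extra trip. The WOMAC A criterion would rest on the Week 12 score, taken shortly before the injection.

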7.9.7. Vital Signs

Vital signs are to be taken at the days indicated in Table 7-2 and Table 7-3.

The following measurements will be taken: sitting blood pressure, heart rate, respiration rate, and oral temperature.

7.9.8. Height, Weight and BMI Determination

Height and weight are to be taken at the days indicated in Table 7-2 and Table 7-3. Height will be measured in centimeters or inches. Weight will be measured in kilograms or pounds. BMI will be calculated using the following formulas (reference: www.cdc.gov):

CONFIDENTIAL Page 51 of 72

Table 7-4: Height, Weight and BMI Determination

Measurement Units	Formula and Calculation			
Kilograms and Meters (or centimeters)	Formula: weight (kg) / [height (m)] ² With the metric system, the formula for BMI is weight in kilograms divided by height in meters squared. Since height is commonly measured in centimeters, divide height in centimeters by 100 to obtain height in meters. Example: Weight = 68 kg , Height = $165 \text{ cm} (1.65 \text{ m})$ Calculation: $68 \div (1.65)^2 = 24.98$			
Pounds and Inches	Formula: weight (lb.) / [height (in)] ² x 703 Calculate BMI by dividing weight in pounds (lbs.) by height in inches (in) squared and multiplying by a conversion factor of 703. Example: Weight = 150 lbs., Height = 5'5" (65") Calculation: $[150 \div (65)^2]$ x $703 = 24.96$			

7.9.9. Central Clinical Laboratory Evaluations

Blood samples will be taken as follows at the days indicated Table 7-2 and Table 7-3. The specific laboratory panels to be run can be found in the table below. Follow the Central Laboratory Manual for detailed sample collection, handling, storage, and shipping instructions. Please see Table 7-5 below.

Table 7-5: Clinical Laboratory Panel

CLINICAL LABORATORY PANELS				
HEMATOLOGY	CLINICAL CHEMISTRY			
Hemoglobin	Sodium			
Hematocrit	Potassium			
Erythrocyte count (RBC)	Bicarbonate			
Mean cell volume	Chloride			
Leukocytes (WBC)	Calcium			
Absolute counts of:	Total bilirubin			
 Neutrophils 	Alkaline phosphatase			
Lymphocytes	Alanine aminotransferase			
• Monocytes	Aspartate aminotransferase			
• Eosinophils	Blood urea nitrogen			
Basophils	Creatinine			
• Platelets	Uric acid			
	Glucose			
INFECTIOUS DISEASES	Total protein			
Hepatitis B Surface Antigen	Albumin			
Hepatitis C Antibody1				
HIV2	ESR: test provided by Central Laboratory but performed and			
PREGNANCY TESTS (WOMEN OF CH	read at the site			

- Serum: submitted to and performed by Central Laboratory
- Urine: test provided by Central Laboratory but performed and read at the site
- 1. Patients positive for HCV Antibody will have reflex testing for circulating HCV RNA.
- 2. HIV screening will use a current 4th generation test for both antibody and viral antigen.

CONFIDENTIAL Page 52 of 72

